15.4.2. Overdose

An overdose is any dose of study treatment given to a subject or taken by a subject that exceeds the dose described in the protocol. Overdoses are not considered AEs and should not be recorded as an AE on the CRF; however, all overdoses must be recorded on an Overdose form and faxed to [REDACTED] within 24 hours of the site becoming aware of the overdose. An overdose must be reported to [REDACTED] even if the overdose does

CONFIDENTIAL

The information contained herein may not be used, disclosed, or published without the written consent of Biogen MA Inc.

not result in an AE. If an overdose results in an AE, the AE must be recorded. If an overdose results in an SAE, both the SAE and Overdose forms must be completed and faxed to [REDACTED] ([REDACTED]). All study treatment-related dosing information must be recorded on the dosing CRF.

15.4.3. Medical Emergency

In a medical emergency requiring immediate attention, study site staff will apply appropriate medical intervention, according to current standards of care. The Investigator (or designee) should contact the [REDACTED] 24-hour emergency medical support number. Refer to the Study Reference Guide's Official Contact List for complete contact information.

15.4.3.1. Unblinding for Medical Emergency

In this study, emergency decoding will be made available to the Investigator and designated personnel at Biogen through IRT.

In a medical emergency when knowledge of the subject's treatment assignment may possibly influence the subject's clinical care, the Investigator may access the subject's treatment assignment by IRT. However, prior to unblinding, the Investigator can contact the [REDACTED] 24-hour emergency medical support number at [REDACTED].

The Investigator must document the reasons for unblinding in the subject's source documents. The Investigator is strongly advised not to divulge the subject's treatment assignment to any individual not directly involved in managing the medical emergency, nor to personnel involved with the analysis and conduct of the study.

15.5. Contraception Requirements

For the purposes of this study, women of childbearing potential are defined as all women physiologically capable of becoming pregnant, UNLESS they meet one of the following conditions:

- Postmenopausal
 - 12 months of natural (spontaneous) amenorrhea without an alternative medical cause or 6 weeks after surgical bilateral oophorectomy with or without hysterectomy.
- Post hysterectomy.
- Female surgical sterilization (e.g., bilateral tubal ligation).

For the purposes of this study, highly effective contraception is defined as use of 1 of the following:

- For females of childbearing potential:
 - Established use of oral, injected, or implanted hormonal methods of contraception.
 - Placement of an intrauterine device or intrauterine system

CONFIDENTIAL

The information contained herein may not be used, disclosed, or published without the written consent of Biogen MA Inc.

- Barrier methods of contraception with use of a spermicide: condom or occlusive cap (diaphragm or cervical/vault caps) with spermicidal foam/gel/film/cream suppository. The use of barrier contraceptives should always be supplemented with the use of a spermicide.
- Male sexual partners underwent surgical sterilization with the appropriate postvasectomy documentation of the absence of sperm in the ejaculate.
- For males:
 - Vasectomy with negative semen analysis at FU.
 - Use of condoms with spermicide.
 - Female sexual partners who underwent surgical sterilization (e.g., bilateral tubal ligation), are postmenopausal, are post-hysterectomy, or are using highly effective contraception as listed above for female subjects.

For males and females of childbearing potential:

True abstinence, when this is consistent with the preferred and usual lifestyle of the subject, can be considered an acceptable method of contraception based on the evaluation of the Investigator who should also take into consideration the duration of the clinical trial. Periodic abstinence (e.g., calendar, ovulation, symptothermal, postovulation methods) and withdrawal are not considered acceptable methods of contraception.

Pregnancy reporting is described in Section 15.4.1.

15.6. Safety Responsibilities

15.6.1. The Investigator

The Investigator's responsibilities include the following:

- Monitor and record all AEs, including SAEs, regardless of the severity or relationship to study treatment.
- Determine the seriousness, relationship, and severity of each event.
- Determine the onset and resolution dates of each event.
- Monitor and record all pregnancies and FU on the outcome of the pregnancy in female subjects.
- Complete an SAE form for each SAE and fax it to Biogen (or designee) within 24 hours of the study site staff becoming aware of the event.
- Pursue SAE FU information actively and persistently. FU information must be reported to Biogen (or designee) within 24 hours of the study site staff becoming aware of new information.

CONFIDENTIAL

The information contained herein may not be used, disclosed, or published without the written consent of Biogen MA Inc.

- Ensure all AE and SAE reports are supported by documentation in the subjects' medical records.
- Pursue AE FU information, if possible, until the event has resolved or become stable.
- Report SAEs to local EC/IRBs, as required by local law.

15.6.2. Biogen

Biogen's responsibilities include the following:

- Before study site activation and subject enrollment, the Clinical Monitor (██████) is responsible for reviewing with study site staff the definitions of AE and SAE, as well as the instructions for monitoring, recording, and reporting AEs and SAEs.
- Biogen (or designee) is to notify all appropriate regulatory authorities, central EC/IRBs, and Investigators of SAEs, as required by local law, within required time frames.

CONFIDENTIAL

The information contained herein may not be used, disclosed, or published without the written consent of Biogen MA Inc.

16. STATISTICAL METHODS AND DETERMINATION OF SAMPLE SIZE

The objectives of the study and the endpoints to be analyzed are listed in Section 6.

16.1. Demography and Baseline Disease Characteristics

Demographics and baseline data will be summarized by treatment group with summary statistics (mean, standard deviation [SD], median, and range) or with frequency distributions.

16.2. Efficacy and Pharmacodynamics

16.2.1. Analysis Population

The intent-to-treat (ITT) population, defined as all subjects who were randomized and received at least 1 dose of study treatment (aducanumab or placebo), will be used for the efficacy analyses. Subjects will be analyzed in the groups to which they were randomized.

16.2.2. Methods of Analysis

16.2.2.1. General Considerations

Summary statistics will be presented. For continuous endpoints, summary statistics will generally include: number of subjects with data, mean, standard deviation, median, and range. For categorical endpoints, this will generally include: number of subjects randomized or dosed, number with data, and the percent of those with data in each category. Statistical testing for efficacy endpoints will be made between each aducanumab dose (high and low) and placebo. All statistical tests will be 2-sided.

16.2.2.2. Aducanumab Doses to be Evaluated

The following aducanumab doses as compared with placebo will be evaluated:

- Aducanumab high-dose (10 mg/kg in ApoE ϵ 4 [including 6 mg/kg for subjects enrolled under protocol versions prior to Version 4 who do not have the opportunity to uptitrate to 10 mg/kg prior to completing Week 78 of the study] and 10 mg/kg in ApoE ϵ 4 non-carriers).
- Aducanumab low-dose (3 mg/kg in ApoE ϵ 4 carriers and 6 mg/kg in ApoE ϵ 4 non-carriers).

In the event that the maximum dose (10 mg/kg) is terminated after the start of the study (Section 5.3.2) the definition of aducanumab high dose and aducanumab low dose will be modified as shown in Table 17. The dosing modification will be entirely based on interim analysis of outcomes that are independent of, and uninformative about, the treatment-related efficacy effect. Control of Type I error rate is thus maintained without a statistical adjustment for such adaptations [Chow and Chang 2011].

CONFIDENTIAL

The information contained herein may not be used, disclosed, or published without the written consent of Biogen MA Inc.

Table 17: Treatment Groups in the Event of High Dose Group Termination

High Dose Group(s) Terminated	Definitions of Revised Treatment (Low/High Dose) Groups for Comparison
ApoE ε4 carrier high-dose group (10 mg/kg) [including 6 mg/kg for subjects enrolled under versions prior to Version 4 who do not have the opportunity to up-titrate to 10 mg/kg prior to completing Week 78 of the study]	Low: ApoE ε4 carrier 3 mg/kg and non-carrier 6 mg/kg High: ApoE ε4 carrier 3 mg/kg and non-carrier 10 mg/kg
ApoE ε4 non-carrier high-dose group (10 mg/kg)	Low: ApoE ε4 carrier 3 mg/kg and non-carrier 6 mg/kg High: ApoE ε4 carrier 10 mg/kg and non-carrier 6 mg/kg
ApoE ε4 carrier high-dose group (10 mg/kg) AND ApoE ε4 non-carrier high-dose group (10 mg/kg)	ApoE ε4 carrier 3 mg/kg and non-carrier 6 mg/kg

16.2.2.3. Considerations for Multiple Comparison Adjustments

A sequential (closed) testing procedure will be used to control the overall Type I error rate due to multiple comparisons for the primary endpoint. The order of treatment comparisons is as follows: aducanumab high-dose versus placebo and aducanumab low-dose versus placebo. All comparisons after the initial comparison with $p > 0.05$ will not be considered statistically significant.

Secondary endpoints have been rank prioritized, in the order shown in Section 6. In order to control for a Type I error for the secondary endpoints, a sequential closed testing procedure will be used and will include both the order of the secondary endpoints and treatment comparisons. Specifically, for each of the secondary endpoints, a sequential (closed) testing procedure, as for the primary endpoint, will be used to control the overall Type I error rate due to multiple treatment comparisons. If statistical significance is not achieved for 1 or 2 comparisons, all endpoint(s) of a lower rank will not be considered statistically significant for 1 or 2, respectively.

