7. STUDY DESIGN

7.1. Study Overview

Study 221AD302 is a multicenter, randomized, double-blind, placebo-controlled, parallel-group Phase 3 study in subjects with early AD, including MCI due to AD and a subset of mild AD, followed by an optional dose-blinded LTE period of up to 5 years. Approximately 1605 subjects (see Section 16.8) will be enrolled across approximately 150 centers globally. The primary study objective is to evaluate the efficacy of monthly doses of aducanumab on the CDR-SB relative to placebo. Secondary objectives include assessment of the effect of monthly doses of aducanumab on clinical progression as compared to placebo. The safety of monthly doses of aducanumab will also be evaluated.

Subjects will receive infusions of aducanumab or placebo approximately every 4 weeks for approximately 18 months (a total of 20 doses). Subjects will be randomized to receive aducanumab low dose:aducanumab high dose:placebo in a 1:1:1 ratio. The randomization will be stratified by site and ApoE ϵ 4 status (carrier or non-carrier). The ratio of ApoE ϵ 4 carriers to non-carriers in the study population will generally reflect the distribution in the broader AD population. Enrollment will also be monitored, via interactive response technology (IRT), such that subjects with mild AD represent a small percentage of the total enrolled in the trial.

At the end of the double-blind, placebo-controlled treatment period, subjects who meet the extension entry criteria may enter a long-term safety and efficacy extension period, with all subjects receiving aducanumab approximately every 4 weeks (up to a total of 65 doses over 5 years). The EOT Visit will occur at Week 338, or when the last subject has had his or her Week 182 Visit, whichever occurs first.

The total duration of study participation for each subject only participating in the placebo-controlled period of the study will be up to approximately 102 weeks, including a series of screening visits within 8 weeks before administration of the first dose, a 76-week placebo-controlled treatment period, and a safety follow-up (FU) period of 18 weeks after the final dose.

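### The by-dose carry-down rule for the secondary endpoints does not deliver the Type I error control that Section 16.2.2.3 claims: worst-case family-wise error within the secondary endpoints is about 9.2% to 9.8%, not 5%

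*Protocol*

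**What the plan says.** Protocol Section 16.2.2.3 (Version 6.0) sets these rules.

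- **Primary endpoint.** The order is "aducanumab high-dose versus placebo and aducanumab low-dose versus placebo", and testing stops at the first failure: "All comparisons after the initial comparison with $p > 0.05$ will not be considered statistically significant".
- **Ranking.** "Secondary endpoints have been rank prioritized, in the order shown in Section 6", which gives MMSE, then ADAS-Cog 13, then ADCS-ADL-MCI (Section 6.2).
- **Doses within a secondary endpoint.** The same high-then-low sequence, "as for the primary endpoint, will be used to control the overall Type I error rate due to multiple treatment comparisons".
- **Carry-down between endpoints.** If one or two comparisons fail, "all endpoint(s) of a lower rank will not be considered statistically significant for 1 or 2, respectively".
- **Claimed property.** "In order to control for a Type I error for the secondary endpoints, a sequential closed testing procedure will be used". The same sentence says that the procedure takes in both the endpoint order and the treatment comparisons.

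Section 16.2.2.1 adds: "All statistical tests will be 2-sided". No sentence divides alpha between the doses or between the endpoints.

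**The concern.** A fixed sequence controls family-wise error because only one hypothesis is open at a time. A closed procedure controls it because every intersection of nulls is tested at level 0.05. The carry-down rule does neither.

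Suppose high dose succeeds on an endpoint. Low dose on that endpoint is now tested at 0.05. High dose on the next endpoint is also tested at 0.05, whether or not low dose succeeded, because a low-dose failure blocks later endpoints for low dose only. The intersection of those two nulls is thus rejected whenever either p-value is at most 0.05, which is not a level-0.05 test. The fork recurs at each rank.

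What is at stake is the confirmatory status of the secondary claims. The protocol presents the set of secondary results across both doses as protected at 0.05. In a plausible pattern for a two-dose trial, where high dose works down to some endpoint and low dose does not, the protection is close to half of what is stated.

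**Working it through.** **The plan's own figure.** Section 16.8 gives 450 per group for about 90% power, from a difference of 0.5, SD 1.92, two-sided 0.05 and 30% drop-out.

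n = 2 × (1.960 + 1.282)² × 1.92² / 0.5² ≈ 310 evaluable per arm; 310 / 0.70 ≈ 443, which agrees with 450. With 450 × 0.70 = 315 evaluable, the standard error is 1.92 × √(2/315) = 0.153, so z = 0.5 / 0.153 = 3.268 and power = Φ(3.268 − 1.960) = 90.5%. The protocol gives no family-wise figure other than the 0.05 threshold.

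**Inputs for the error check**
- Alpha 0.05 two-sided for every test (Sections 16.2.2.1 and 16.2.2.3).
- Correlation 0.5 between the two dose-versus-placebo tests on one endpoint. This follows from the shared placebo arm and equal allocation in Section 7.1: "Subjects will be randomized to receive aducanumab low dose:aducanumab high dose:placebo in a 1:1:1 ratio".
- Between-endpoint correlation r: not in the protocol, so assumed, range 0 to 0.9. Low dose on one endpoint and high dose on the next then correlate at 0.5 × r.

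**The rule as coded.** Number the endpoints 1 CDR-SB, 2 MMSE, 3 ADAS-Cog 13, 4 ADCS-ADL-MCI, and write H for high dose and L for low dose. H on endpoint k requires H on endpoint k−1. L on endpoint k requires both H on endpoint k and L on endpoint k−1. Success on CDR-SB for the same dose is taken as a precondition for MMSE.

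**One fork.** If L on endpoint k and H on endpoint k+1 are both null and both reached, the error is P(|Z₁| > 1.96 or |Z₂| > 1.96). With independent tests this is 1 − 0.95² = 9.75%. With correlation:

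| r | 0.5 × r | Each at 0.05 | Each at 0.025 |
|---|---|---|---|
| 0 | 0 | 9.75% | 4.94% |
| 0.3 | 0.15 | 9.69% | 4.91% |
| 0.5 | 0.25 | 9.59% | 4.87% |
| 0.7 | 0.35 | 9.43% | 4.80% |
| 0.9 | 0.45 | 9.21% | 4.71% |

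**The whole rule, simulated** (4 endpoints × 2 doses, 500,000 runs per scenario)

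| Truth | r = 0 | r = 0.5 | r = 0.7 |
|---|---|---|---|
| Secondary family only: H1, L1, H2 strongly effective, rest null | 9.7% | 9.7% | 9.4% |
| Primary and secondary jointly: only H1 effective, near-certain power | 9.7% | 9.6% | 9.4% |
| Primary and secondary jointly: only H1 effective, 90% power | 8.2% | 7.5% | 6.8% |
| Everything null | 5.0% | 5.0% | 5.0% |

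At r = 0.9 the first three rows are 9.2%, about 9.3% and 6.1%. In the same scenarios a strict single sequence (H1, L1, H2, L2 and so on) never exceeded 5.0% beyond simulation error.

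**The case against.** The case for the rule has real weight, and most of its limits stand.

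- **The doses do not run freely in parallel.** Low dose always needs a high-dose success on the same endpoint. That is correct. The leak is only that high dose goes on after low dose has failed. The requirement does not lower the maximum, because the maximum arises where high dose has succeeded.
- **No individual claim is made at twice the nominal rate.** A reader might infer that a single low-dose or high-dose claim carries about 10% error. The documents do not support that: each test is at 5%, and only the chance of at least one false claim among several rises. Low-dose CDR-SB belongs to the primary sequence, which is valid at 0.05.
- **The figure is a worst case.** If everything is null the error is 5.0%. The figure also counts rejections in either direction; false claims of benefit alone are about 4.6% to 4.9% against a nominal 2.5%.
- **Separate families.** The section claims control for the primary endpoint and for the secondary endpoints separately, so the joint primary-and-secondary scenarios do not contradict it. The within-secondary scenario does. It is narrow, but control that holds only for some patterns of true effect is not what the section promises.
- **The primary as a precondition.** A reader might infer that secondary endpoints may be tested even when CDR-SB fails. The section does not say so. It is silent, and that detail is commonly left to the SAP, so no finding is made of it.

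The SAP is not at hand and may tighten the rule. The protocol nevertheless states both the rule and what it achieves, and the two do not agree.

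**Conclusion.** The point holds in this form: the by-dose carry-down does not control Type I error over endpoint order and dose comparisons together, as Section 16.2.2.3 says it does. Within the secondary endpoints alone the two-sided family-wise error can reach about 9.2% to 9.8%. This rests on three assumptions: between-endpoint correlation of 0 to 0.9, which the protocol does not give; high power for the truly effective comparisons; and the primary as a precondition for the same dose. Counted jointly with the primary endpoint, the maximum is similar, and about 6% to 8% when only high-dose CDR-SB is effective at its planned 90% power.

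The high-dose and low-dose tests on CDR-SB are unaffected, and every single test remains at 5%. It should be fixed, as a wrong statement about the secondary claims. It is not a defect of the primary analysis.

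**What to change.** Amend Section 16.2.2.3 before any unblinding, including the optional interim superiority look in Section 16.7.2. Any one of three changes would do.

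1. **Split alpha where the paths fork (preferred).** For control within the secondary family, test high-dose MMSE at 0.05. After it succeeds, give 0.025 to the low-dose path (MMSE onward) and 0.025 to the high-dose path (ADAS-Cog 13 onward), with recycling if a path is completed. The primary sequence is untouched. The fork error falls to 4.7% to 4.9%. If joint control with the primary is wanted, the split must start after high-dose CDR-SB. Low-dose CDR-SB is then tested at 0.025, and its power at a true difference of 0.5 drops from 90.5% to Φ(3.268 − 2.241) = 84.8%, unless recycling restores the alpha.
2. **One serial order.** Test high then low within each ranked endpoint and stop at the first failure. This gives 5.0%, but all later high-dose claims are lost whenever low dose fails. With 315 evaluable per arm, SD 1.92 and a true high-dose effect of 0.5, low dose fails on CDR-SB in about 60%, 33% or 7% of trials in which high dose succeeds, for assumed low-dose effects of 0.25, 0.35 or 0.5 (the protocol gives none). That is a substantial cost unless the low dose is about as effective as the high dose.
3. **Keep the rule and correct the claim.** State that error is controlled at 0.05 within each dose, not across doses and endpoints together. This costs no power but gives up the stronger statement.

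All three change wording only, with no effect on conduct or data collection.

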16.2.2.4. Analysis of the Primary Endpoint

The population for the primary endpoint analysis will be subjects in the ITT population. A mixed model repeated measures (MMRM) model will be used as the primary analysis to analyze change from baseline CDR-SB using fixed effects of treatment, time, treatment-by-time interaction, baseline CDR-SB, baseline CDR-SB by time, baseline MMSE, AD symptomatic medication use at baseline, region, and laboratory ApoE ε4 status.

CONFIDENTIAL

The information contained herein may not be used, disclosed, or published without the written consent of Biogen MA Inc.

16.2.2.5. Analysis of the Secondary Endpoints

16.2.2.5.1. Change From Baseline to Week 78 in MMSE

The population for the analysis will be subjects in the ITT population. A MMRM model will be used as the primary analysis to analyze change from baseline MMSE using fixed effects of treatment, time, treatment-by-time interaction, baseline MMSE value, baseline MMSE by time interaction, AD symptomatic medication use at baseline, region, and laboratory ApoE ϵ 4 status.

16.2.2.5.2. Change From Baseline to Week 78 in ADAS-Cog 13

The population will be subjects in the ITT population. An MMRM model will be used as the primary analysis to analyze change from baseline ADAS-Cog 13 using fixed effects of treatment, time, treatment-by-time interaction, baseline ADAS-Cog 13, baseline ADAS-Cog 13 by time interaction, baseline MMSE, AD symptomatic medication use at baseline, region, and laboratory ApoE ϵ 4 status.

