8. SELECTION OF SUBJECTS

8.1. Inclusion Criteria

To be eligible to participate in this study, candidates must meet the following eligibility criteria at Screening or at the timepoint specified in the individual eligibility criterion listed:

1. Ability to understand the purpose and risks of the study and provide signed and dated informed consent and authorization to use confidential health information in accordance with national and local subject privacy regulations.
2. Aged 50 to 85 years old, inclusive, at the time of informed consent.
3. All women of childbearing potential and all men must practice highly effective contraception during the study and for 24 weeks after their last dose of study treatment. For further details of contraceptive requirements for this study, please refer to Section 15.5.
4. Must have at least 6 years of education or work experience to exclude mental deficits other than MCI or mild AD.
5. Must have a positive amyloid PET scan. Previously obtained PET scan (within 12 months of Screening) is permissible for subjects not participating in the amyloid PET substudy. Previous PET scan images must be submitted to the central imaging vendor to confirm study inclusion criteria are met.
6. Must meet all of the following clinical criteria for MCI due to AD or mild AD according to NIA-AA criteria [Albert 2011; McKhann 2011], and must have:
 - A CDR global score of 0.5.
 - An RBANS score of 85 or lower indicative of objective cognitive impairment (based upon the Delayed Memory Index score).
 - An MMSE score between 24 and 30 (inclusive).
7. Apart from a clinical diagnosis of early AD, the subject must be in good health as determined by the Investigator, based on medical history and screening assessments.
8. Must consent to ApoE genotyping.
9. Has one informant/care partner who, in the Investigator's opinion, has frequent and sufficient contact with the subject as to be able to provide accurate information about the subject's cognitive and functional abilities. The informant/care partner must minimally be available by phone to provide information to the Investigator and study staff about the subject and agrees to attend in person clinic visits that require partner input for scale completion. An informant/care partner should be available for the duration of the study, and the use of the same informant/care partner for the duration of the study is encouraged.

CONFIDENTIAL

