9.2. Randomization and Registration of Subjects

Subjects will be registered at the Screening Visit and randomized only after all baseline assessments have been completed and the Investigator has verified that the subjects are eligible per criteria in Sections 8.1 and 8.2. No subject may begin treatment prior to assignment of a unique identification number (registration) and randomization. Any subject identification numbers or randomization schedule assignments that are assigned will not be reused even if the subject does not receive treatment. Rescreened subjects will be assigned a new number.

Subjects will be randomized to receive aducanumab low dose:aducanumab high dose:placebo in a 1:1:1 ratio. The randomization will be stratified by site and ApoE ϵ 4 status (carrier or non-carrier). Subjects randomized to placebo at the start of the placebo-controlled period will also be randomized to receive dose-blinded aducanumab (low dose:high dose, 1:1 ratio) for the LTE period and randomization will be stratified by subject ApoE ϵ 4 carrier status. Treatment group assignments for the placebo-controlled period and the LTE period will be assigned at Study Day 1. Enrollment will be monitored, via the IRT, such that the population of subjects with mild AD represents a small percentage of the total enrolled in the trial. Subjects who withdraw from the study may not be replaced.

Refer to the Study Reference Guide for details on registration and randomization.

CONFIDENTIAL

The information contained herein may not be used, disclosed, or published without the written consent of Biogen MA Inc.

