16.2.2.5.3. Change From Baseline to Week 78 in ADCS-ADL-MCI

The population will be subjects in the ITT population. An MMRM model will be used as the primary analysis to analyze change from baseline ADCS-ADL-MCI using fixed effects of treatment, time, treatment-by-time interaction, baseline ADCS-ADL-MCI, baseline ADCS-ADL-MCI by time interaction, baseline MMSE, AD symptomatic medication use at baseline, region, and laboratory ApoE ϵ 4 status.

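### The MMSE model, for the first-ranked secondary endpoint, is the only listed efficacy MMRM without a second baseline severity measure; adding baseline ADAS-Cog 13 would buy a little precision at almost no cost

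*Protocol*

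**What the plan says.** Protocol Version 6.0 lists the fixed effects of each efficacy MMRM in full, so the covariate set is fixed in the protocol. (The SAP was not at hand for this check.)

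- Section 16.2.2.5.1 (MMSE): treatment, time, their interaction, and "baseline MMSE value, baseline MMSE by time interaction, AD symptomatic medication use at baseline, region, and laboratory" ApoE ε4 status.
- Section 16.2.2.4 (CDR-SB, primary): among the covariates, "baseline CDR-SB, baseline CDR-SB by time, baseline MMSE, AD symptomatic medication use at baseline".
- Section 16.2.2.5.2 (ADAS-Cog 13): "baseline ADAS-Cog 13, baseline ADAS-Cog 13 by time interaction, baseline MMSE", then the same remaining terms.
- Section 16.2.2.5.3 (ADCS-ADL-MCI): "baseline ADCS-ADL-MCI, baseline ADCS-ADL-MCI by time interaction, baseline MMSE", then the same remaining terms.
- Section 16.2.2.6.1 (tertiary endpoints): the same pattern, own baseline plus baseline MMSE.

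Section 16.2.2.3 ranks the secondary endpoints in the order of Section 6, and Section 6.2 lists MMSE first. If a dose comparison is not significant on an endpoint, lower-ranked endpoints cannot be declared significant for that comparison.

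On the data available: Table 1 schedules MMSE before dosing only at Screening Visit 1, where it is also an entry test (24 to 30, Section 8.1). Section 7.3.1 places ADAS-Cog 13 at Screening Visit 2, within 20 days and not on the MMSE day. Section 9.2 says subjects are "randomized only after all baseline assessments have been completed".

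**The concern.** The other models use a second baseline measure of severity, so the sponsor evidently thinks one worth having. In the MMSE model the common covariate list loses that term because baseline MMSE is already the endpoint's own baseline. What is left is one screening score, measured with error.

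A second cognitive scale taken on another day, also measured with error, would normally carry further information about where a subject truly stands, and so about the Week 78 score. Leaving it out costs precision. The place matters more than the amount: MMSE is the gate to ADAS-Cog 13 and ADCS-ADL-MCI for each dose comparison, so power lost on MMSE is passed down the chain.

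**Working it through.** **Step 1. The models side by side (Protocol 16.2.2.4 to 16.2.2.6.1).**

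| Endpoint | Own baseline and own baseline by time | Second severity measure |
|---|---|---|
| CDR-SB | yes | baseline MMSE |
| MMSE | yes | none |
| ADAS-Cog 13 | yes | baseline MMSE |
| ADCS-ADL-MCI | yes | baseline MMSE |
| Tertiary MMRM | yes | baseline MMSE |

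AD medication use, region and ApoE ε4 status are in all five.

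**Step 2. The plan's own figure.** Section 16.8 gives a difference of 0.5, SD 1.92, two-sided 0.05, 90% power and 30% drop-out for CDR-SB.

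n per arm = 2 × (1.960 + 1.282)² × 1.92² / 0.5² = 310 evaluable; 310 / 0.70 = 443, against 450 planned. With 450 × 0.70 = 315 evaluable per arm, power is 90.4% (noncentral t). The primary figure reproduces and is not in question. The protocol states no SD, effect or power for MMSE.

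**Step 3. Effect of one more covariate.** Let ρ be the partial correlation of baseline ADAS-Cog 13 with Week 78 MMSE change, given the covariates already in the model. Adding it multiplies the standard error by √(1 − ρ²), which is equivalent to 1/(1 − ρ²) times as many subjects. This is the single-visit ANCOVA result, used as an approximation to the MMRM contrast at Week 78.

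At the current size, 535 × 0.70 = 374.5 evaluable per arm, the standard error under the stated model is √(2/374.5) = 0.0731 residual SDs. A comparison with 80% power has noncentrality 1.960 + 0.842 = 2.802, and the new power is Φ(2.802/√(1 − ρ²) − 1.960).

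| ρ (assumed) | SE smaller by | As if more subjects | 80% power becomes |
|---|---|---|---|
| 0 | 0 | 0 | 80.0% |
| 0.1 | 0.5% | 1.0% | 80.4% |
| 0.2 | 2.0% | 4.2% | 81.6% |
| 0.3 | 4.6% | 9.9% | 83.6% |
| 0.4 | 8.3% | 19.0% | 86.4% |

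Break-even: with about 3 × 374.5 − 10 = 1113.5 residual degrees of freedom, the covariate pays for itself once |ρ| exceeds √(1/1113.5) = 0.03, or √(2/1113.5) = 0.04 if chance imbalance is counted.

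**Step 4. A plausible range for ρ.** All inputs here are assumptions. S is a standard normal latent severity.

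- Baseline MMSE: 26 − 2.2·S plus error SD 1.5, rounded and capped at 30.
- Baseline ADAS-Cog 13: 22 + 5·S plus error SD 4.
- Week 78 MMSE: a fresh MMSE reading minus (3.3 + b·S), with further SD 3.0, capped at 30; b from 0 to 1.0.

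| | R² of baseline MMSE for Week 78 MMSE | Size of ρ | SE smaller by |
|---|---|---|---|
| No entry cut | 0.20–0.32 | 0.21–0.28 | 2.1–3.9% |
| MMSE at least 24 | 0.13–0.21 | 0.21–0.28 | 2.2–4.0% |

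The cut weakens baseline MMSE as a predictor but leaves ρ almost unchanged.

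A second set of assumptions used MMSE signal SD 2, MMSE error SD 1.2–1.6, ADAS-Cog error SD 4–5 on a signal SD of 6, decline SD 2.5–3.5, and correlation of decline with severity 0.2–0.4. It cut residual variance by 3.7–14.6% with the MMSE cut alone. It cut it by 2.2–8.5% when a further noisy severity band stood in for the CDR and RBANS entry criteria. In the latter case the standard error is 1 − √(1 − 0.022) = 1.1% to 1 − √(1 − 0.085) = 4.3% smaller.

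**The case against.** The strongest reply is that nothing here is wrong. One covariate rule is applied throughout, and for MMSE two of its items coincide, so the list is one shorter by construction. The model is pre-specified, adjusts for its own baseline and that baseline's interaction with time, is unbiased under randomization and controls Type I error. Another prognostic covariate could be proposed for almost any model. All of this stands, and it limits the point to efficiency.

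The size can also be challenged. The protocol contains no MMSE variance or correlation. AD medication use, region and ApoE ε4 status may already carry some severity information, and the CDR and RBANS entry criteria narrow the range that ADAS-Cog 13 could explain. This stands too and is why the lower figures are used.

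There are practical objections. Study 221AD301 is described as identically designed, so a change here alone would break alignment. A subject with a missing baseline covariate would drop out of the model. Both can be met in the text of the change; neither is a reason to leave the covariate out.

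A reader might infer that the 24 to 30 entry range is the cause. The calculation does not support that: the partial correlation is about the same with and without the cut. A reader might also reach a gain of up to 9% in the standard error, or 21% more subjects. That needs a variance reduction of about 17.6%, which one latent model gives under favourable assumed error SDs with the other entry gates ignored. The documents give no basis for it.

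**Conclusion.** The point holds as a modest, inexpensive gain in efficiency. The MMSE model is the only listed efficacy MMRM without a second baseline severity measure, the protocol gives no reason, and a suitable measure is already scheduled for everyone before randomization.

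The size rests wholly on an assumed partial correlation. At 0.2 to 0.3 the Week 78 standard error is about 2 to 5% smaller; the simulations that vary the assumptions and add the other entry gates put it at about 1 to 4%; at 0 there is no gain. The effect on the lower-ranked endpoints, through the testing order, cannot be quantified from the protocol.

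It would be wrong to read this as bias, loss of Type I error control, or a weakness of the primary analysis. Nor does it argue for changing the CDR-SB model, which already has baseline MMSE as its second measure.

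**What to change.** In Section 16.2.2.5.1 (and the matching SAP text), add baseline ADAS-Cog 13 and baseline ADAS-Cog 13 by time to the fixed effects. Fix this before any unblinded interim look under Section 16.7.

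State a rule for an isolated missing baseline ADAS-Cog 13, for example imputing the overall mean without regard to treatment, so that no ITT subject is dropped. Make the same change in Study 221AD301. Leave Section 16.2.2.4 as it is. If the sponsor prefers the present model, a sentence giving the reason would be enough.

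The cost is the amendment text in two studies and three model parameters (one slope for each of Weeks 26, 50 and 78). No new data, visits or subjects are needed.
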